#### *Missing values*

No imputation will be performed for missing data.

## 4.7 ACEND

The ACEND includes a total of seven domains assessing physical impact (including feeding/grooming/dressing, sitting/play, transfers, and mobility) and general caregiver impact (including time, emotion, and finance) and each domain comprises several items. All the ACEND scores will be listed and not summarized for this analysis being the data collected only after the latest version of the protocol.

The ACEND includes a total of seven domains assessing physical impact (including feeding/grooming/dressing, sitting/play, transfers, and mobility) and general caregiver impact (including time, emotion, and finance) and each domain comprises several items. The total score for a domain with  $n$  items, each item assessed on ordinal scale from 1 to  $z$ , is derived as follows: 100 multiplied by (Mean of the  $n$  items in the domain - 1) divided by ( $z-1$ ). This total score will be on a scale of 0 to 100 with a higher score indicating a greater impact on the caregiver. At least two items for the time domain and one item for the remaining domains need to be non-missing for a total to be calculated; else the total score will be set to be missing.

## 4.8 Biomarkers

CSF and plasma samples collected as outlined in the schedule of events will be tested for pNf-H concentration.

Baseline pNf-H is defined as the most recent non-missing measurement collected prior to the first dose or Day 1. If any pNf-H measurement is non-missing prior to the first dose, the value closest to and prior to the first dose is used as baseline value. If no pNf-H measurement is available prior to the first dose but any non-missing pNf-H measurement on Day 1 is collected, the value closest to the first dose on Day 1 is used as baseline value.

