After informed consent is obtained, subjects will undergo a screening evaluation no greater than 28 days prior to administration of the first dose of study treatment. Subjects who meet the eligibility criteria will be randomized to receive Nusinersen or sham procedure. Subjects will be admitted to the study site on Part 1 Day 1, undergo predose evaluations, and then receive an LP injection of study treatment or sham procedure. Subjects will return to the study site on Days 15, 29, 64, 183, and 302 for follow-up evaluations and subsequent injections or sham procedures. For subjects receiving Nusinersen or sham procedure, a CSF sample will be taken predose on each injection day in a manner that maintains the blind.

After the study treatment dosing or sham procedure on Day 1, subjects will remain at the study site for at least 24 hours for safety monitoring. Following all subsequent injections, all subjects will remain at the study site for at least 6 hours postdose for safety monitoring.

Safety monitoring will occur on the day following each injection of study treatment or sham procedure. Subjects receiving the dosing or sham procedure on Days 15, 29, 64, 183, and 302 will be monitored by telephone contact on Days 16, 30, 65, 184, and 303.

In addition, subjects will also be monitored through telephone contact throughout the duration of the study.

An End of Part 1 Evaluation will occur up to 4 months after the last dose of Nusinersen or sham procedure, or sooner (if the Sponsor decides to terminate Part 1 early based on emergent data from the Nusinersen clinical development program, as described below). Subjects who terminate early from Part 1 of the study will be encouraged to complete the End of Part 1 Evaluation assessments at the time of withdrawal.

After completing End of Part 1 Evaluation assessments according to the study schedule or sooner, if emergent data from the Nusinersen clinical

CONFIDENTIAL

The information contained herein may not be used, disclosed, or published without the written consent of Biogen MA Inc.

development program necessitate the early termination of Part 1 by the Sponsor, all eligible subjects may elect to enroll in Part 2. All subjects enrolled in the study at the time that the Sponsor terminates Part 1 will be considered Part 1 completers. The next study evaluation for those subjects will serve as an End of Part 1 Evaluation, which may occur at any time prior to the next scheduled Part 1 study evaluation.

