eligible for Study ISIS 396443-CS4. The maintenance dose interval (once every 4 months) was selected based on the estimated spinal tissue and CSF drug half-life (4 to 6 months) and was selected to maintain spinal cord tissue levels of Nusinersen at a steady-state level within the estimated pharmacologically active range. In Part 1, maintenance doses will be given on Day 183 and Day 302, for a total of 6 doses over approximately 10 months. Subjects who were receiving Nusinersen in Part 1 will continue receiving maintenance doses in Part 2 every 4 months. Subjects who were receiving sham in Part 1 will receive maintenance doses starting on Day 183 of Part 2.

Table 1 Nusinersen Dose Volume To Be Injected

Age	Estimated CSF Volume (mL)	Injection Volume (mL)	Dose (mg)
0-3 months (0-90 days)	120	4	9.6
3-6 months (91-182 days)	130	4.3	10.3
6-12 months (183-365 days)	135	4.5	10.8
12-24 months (366-730 days)	140	4.7	11.3
>24 months (>730 days)	150	5.0	12.0

Source: [[Matsuzawa 2001](#)]

CSF = cerebrospinal fluid.

Study Location: Global, multicenter

Number of Planned Subjects: In Part 1, up to 21 subjects are planned (14 Nusinersen; 7 sham procedure).

In Part 2, up to 21 subjects are planned (21 Nusinersen).

Study Population: Part 1 of this study will be conducted in subjects who have clinical signs and symptoms of SMA at ≤ 6 months of age or at > 6 months of age and who are not eligible for the clinical studies ISIS 396443-CS3B or ISIS 396443-CS4.

Part 2 will include only subjects who participated in Part 1 and completed their End of Part 1 Evaluation assessments. Subjects enrolling in Part 2 must meet the Part 2-specific criteria.

Detailed eligibility criteria are described in Section 8.

CONFIDENTIAL

The information contained herein may not be used, disclosed, or published without the written consent of Biogen MA Inc.

Treatment Groups:	
In Part 1, subjects will receive either Nusinersen intrathecally or sham-procedure control in a 2:1 ratio. Randomization will be balanced for the stratification factor (age of symptom onset >6 months versus ≤6 months). A single dose level of 12 mg Nusinersen will be scaled by age at the time of dosing for each subject.
 
In Part 2, all subjects will receive open-label Nusinersen. A single dose level of 12 mg Nusinersen will be scaled by age at the time of dosing for each subject.

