11.1.2. Sham Procedure

In Part 1 of the study, subjects randomized to the sham procedure control group will undergo a sham procedure, rather than study treatment administration, on Study Days 1, 15, 29, 64, 183, and 302. Details regarding the sham procedure will be provided in the DHA. The sham procedure will be administered by dedicated study personnel who are unblinded to treatment group; this cannot be any of the key study site personnel (i.e., the Investigator, study coordinator, or outcomes assessors). The sham procedure in Part 1 will be performed in a dedicated room, and key study personnel and the parent or legal guardian will not be present during the procedure to ensure blinding.

In general, the sham procedure in Part 1 will consist of a small needle prick on the lower back at the location where the LP injection is normally made. The needle will break the skin, but no LP injection or needle insertion will occur. The needle prick will be covered with the same bandage that is used to cover the LP injection normally, thus simulating the appearance of an LP injection. If institutional guidelines require the use of anesthesia or sedation for an LP procedure in Nusinersen-treated subjects, then in order to maintain the blind, minimal sedation (i.e., a low dose of an anxiolytic) should be used for the sham procedure in Part 1, following institutional procedures. The study subject will be kept in the procedure room for the same amount of time that subjects administered study treatment are kept, thus simulating the time period of the study treatment administration procedure.

Study treatment and sham kits will be packaged in a blinded fashion. Blinded kits for the sham procedure in Part 1 contain artificial CSF (5.0 mL solution per 6 mL vial) that will not be injected but will be used to simulate CSF samples for that subject.

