Summary statistics will be presented throughout. For continuous endpoints, summary statistics will generally include number of subjects with data, mean, standard deviation, median, minimum and maximum. The mean changes from baseline will be estimated with 95% confidence intervals. For categorical endpoints, summary statistics will generally include: number of subjects dosed, number of subjects with data, and the percentage of those with data in each category. Frequency distributions will be presented as appropriate.

The statistical software, SAS® version 9.4 or above, will be used for all summaries and statistical analyses.

For Part 2, a limited number of summaries will be produced. The approach will be to preserve the Part 1 study groupings as follows for Safety and Efficacy population:

- Previous control.
- Previous ISIS 396443.
- Total (previous control and previous ISIS 396443).

For the integrated analyses, the Safety displays will be grouped as follows:

- Previous control, Part 1, from their first sham procedure in Part 1.
- Previous control, Part 2, from their first ISIS 396443 dose in Part 2.
- Previous ISIS 396443, Part 1 and 2, from their first ISIS 396443 dose in Part 1.
- Total (Previous control Part 2 and previous ISIS 396443 Part 1 and 2)

For the integrated analyses, the Efficacy displays will be grouped as follows:

- Previous control, Part 1, from their first sham procedure in Part 1.
- Previous control, Part 2, from their first ISIS 396443 dose in Part 2.
- Previous control, Part 1 and 2, from their first sham procedure in Part 1.
- Previous ISIS 396443, Part 1 and 2, from their first ISIS 396443 dose in Part 1.

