### 4.8.1 pNf-H concentration and change in pNf-H

Baseline pNf-H concentrations will be summarized overall, by age of onset using descriptive statistics. Spearman correlation coefficients between baseline pNf-H and one of the baseline measurements (Baseline weight, Age at first dose, gestational age, HINE motor milestones score) and the corresponding  $p$ -values testing whether such correlation is equal to zero will be presented

Summary tables will be presented for pNf-H concentration, change and percentage change from baseline pNf-H by visit. A plot of mean over time will be presented for pNf-H concentration on the semi-logarithmic scale. The mean change from baseline and percentage change from baseline, respectively will be presented on the original scale.

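### SAP 4.8 sends scheduled CSF for pNf-H testing with no exclusion, but the sham children's Part 1 CSF tubes hold artificial kit fluid, so those results are not patient values

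*SAP*

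**What the plan says.** **Sampling.** The Protocol Synopsis says: "For subjects receiving Nusinersen or sham procedure, a CSF sample will be taken predose on each injection day in a manner that maintains the blind". Protocol Table 5 and SAP Table 3 put these samples at Days 1, 15, 29, 64, 183 and 302 of Part 1, for both arms.

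**Source of the sham samples.** Protocol 11.1.2 says of the sham procedure: "The needle will break the skin, but no LP injection or needle insertion will occur". The sham kit holds artificial CSF that "will not be injected but will be used to simulate CSF samples for that subject".

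**Biomarker testing.** SAP 4.8: "CSF and plasma samples collected as outlined in the schedule of events will be tested for pNf-H concentration". Baseline pNf-H is the latest non-missing value before the first dose or Day 1, with a fallback to a Day 1 value if nothing precedes the dose. The section does not say whether a sham procedure counts as a first dose, or which part's Day 1 is meant.

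**Outputs.** SAP 4.8.1: "Baseline pNf-H concentrations will be summarized overall, by age of onset using descriptive statistics". It adds Spearman correlations, with p-values, of baseline pNf-H against baseline weight, age at first dose, gestational age and HINE score. It also plans by-visit tables of level, change and percentage change, and a semi-logarithmic plot. It names neither the matrix (CSF or plasma) nor the treatment grouping.

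**Grouping.** The integrated efficacy groups in SAP 2 include "Previous control, Part 1 and 2, from their first sham procedure in Part 1", and also a Part 2 control group that starts at the first nusinersen dose.

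**The concern.** For a drug assay, artificial CSF does little harm, because zero is also the true nusinersen level in a sham child. pNf-H is the child's own protein, and a tube of kit fluid carries no information about it. Sections 2, 4.8 and 6 of the SAP contain no rule that excludes, flags or sets to missing the sham children's Part 1 CSF. A silent filter cannot be presumed either, because SAP 6.1 plans to tabulate sham CSF concentrations as data.

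Two kinds of output are exposed. By-visit CSF summaries would show untreated children with little or no pNf-H beside treated children. Where a kit-fluid value also serves as baseline, change from baseline and the baseline correlations would be wrong as well. Those correlations are the only place where I find p-values planned in the SAP.

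**Working it through.** **1. Allocation.** The Protocol Synopsis plans up to 21 children at 2:1. Sham = 21/(2+1) = 7; nusinersen = 21 - 7 = 14. This reproduces the stated 14 and 7.

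**2. Artificial samples on the schedule.**
- Part 1: sham 7 × 6 = 42; both arms 21 × 6 = 126; 42/126 = 33.3%.
- Full planned schedule, adding Part 2 (7 CSF samples per former-nusinersen child, 10 per former-sham child): 14 × (6+7) + 7 × (6+10) = 182 + 112 = 294; 42/294 = 14.3%.
- These are upper limits. SAP 2 says Part 1 ended early, with sham children leaving first. Biomarker use of leftover CSF is optional and by consent.

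**3. Artificial CSF baselines, by reading of first dose in SAP 4.8.**
- *Reading A, the first sham procedure counts.* SAP 3.2 and SAP 5 define baseline this way, and SAP 4.1 labels study days up to 1 as Baseline in the integrated windows. Result: 7/21 = 33.3%.
- *Reading B, first nusinersen dose only.* The Part 2 schedule requires a predose CSF sample on Part 2 Day 1, and that is real CSF. Result: 0/21. If that sample is missing, the latest earlier CSF value is kit fluid again.

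**4. Consequences for CSF under Reading A.** The documents do not give the composition of the kit fluid or a rule for pNf-H results below quantification. The figures below assume that the fluid reads at the assay minimum.
- Mean baseline: with kit fluid at 0 and equal true arm means m, the overall mean is (14m + 7 × 0)/21 = 2m/3.
- Percentage change: undefined if kit fluid is set to 0, and a zero cannot be drawn on a log axis. If it is set to a lower limit L, a constant true level T shows as 100 × (T - L)/L: +100% for T = 2L, +9900% for T = 100L.
- Timing: the step appears first in the Part 2 Day 1 sample, which is taken before nusinersen. It then carries into every later visit of the joined control series.

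**5. Spearman correlations under Reading A.** Simulation of 21 children, bivariate normal, with 7 values replaced by a tied minimum (10,000 runs per row). The true correlations are assumptions; the documents give none.

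| True rho | Mean estimate, 21 real | Mean estimate, 7 tied | p<0.05, 21 real | p<0.05, 7 tied | p<0.05, 14 real only |
|---|---|---|---|---|---|
| -0.5 | -0.46 | -0.21 | 60% | 15% | 41% |
| -0.6 | -0.56 | -0.25 | 79% | 19% | 58% |
| -0.7 | -0.66 | -0.29 | 93% | 26% | 78% |

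The mean estimate from the 14 real samples alone is -0.45, -0.55 and -0.65. Dropping the kit-fluid values therefore costs precision but restores the estimate.

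**6. Under Reading B.** Steps 4 and 5 fall away when the Part 2 Day 1 sample exists. The Part 1 sham CSF level at each visit is still kit fluid, so those by-visit summaries fail under both readings.

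**The case against.** The strongest reply is that SAP 4.8 already gives the right baseline. It says first dose, while SAP 2, 3.2 and 5 add the sham procedure when they mean to include it. On that wording a former-sham child's baseline is the Part 2 Day 1 predose CSF. This is a fair reading but not a secure one, because SAP 3.2 also speaks of age at Part 1 first dose for all children. A reader might infer that a third of CSF baselines are certainly artificial. The documents support only a range of 0 to 7 of 21.

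A reader might also infer that pNf-H will appear to rise because of nusinersen. That goes too far. Any step precedes the drug, it needs a Part 1 kit-fluid value as baseline, and it is absent from the Part 2 control group re-based at Part 2 Day 1. SAP 4.8.1 does not say which grouping it will use, and the windowing list in SAP 4.1 does not name pNf-H.

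The matrix is open too. The Day 1 fallback in SAP 4.8 suits plasma, which Table 5 schedules 4 hours after dosing, better than CSF, which is always scheduled predose. If the correlations use plasma, they are untouched. Finally, pNf-H is not among the endpoints listed in Protocol 6 or in the SAP. These points limit the consequences. None of them makes the sham Part 1 CSF a patient sample.

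**Conclusion.** The plan is wrong as written on one point under either reading: CSF pNf-H results for sham children in Part 1 are not patient values and should not be analysed, up to 42 of 126 scheduled Part 1 CSF samples. Damage to baselines (0 to 7 of 21), an artefactual step in the joined control series and weaker CSF correlations follow only if the sham procedure counts as first dose. The correlation figures also need CSF as the matrix, kit-fluid results tied at the minimum, and an assumed true rho. The one-third understatement of the mean further needs a reading of zero and equal true arm means. Plasma pNf-H is sound, and no primary or secondary endpoint depends on this. It should be corrected, but it does not threaten the main conclusions.

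**What to change.** In SAP 4.8 and 4.8.1:
- Exclude all sham-arm Part 1 CSF from pNf-H tables, plots and correlations; use plasma alone for sham pNf-H in Part 1.
- Define the former-sham CSF baseline as the Part 2 Day 1 predose sample, and set it to missing if that sample is absent.
- Name the matrix and the treatment grouping for every output, with CSF and plasma in separate tables.
- Run CSF baseline correlations in the nusinersen arm at Part 1 Day 1 (n up to 14). If former-sham children are added at Part 2 Day 1, show them separately or by study part, because the two baselines fall at different study times. Use their last Part 1 HINE, since HINE is not scheduled on Part 2 Day 1; SAP 4.5.1 already takes the Part 2 HINE baseline from there.

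The cost is a few sentences and a programming filter on arm and study part. Children are unblinded for Part 2, so the arm is known, and no new data are needed. The price is a smaller n for the CSF baseline correlations: in the illustration at rho -0.6, a 58% chance of p<0.05 with 14 real samples, against 79% if all 21 had been real and 19% with kit fluid left in.

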- ⁹ At the evaluations scheduled for injection of study treatment or sham procedure, subjects will be assessed for the following growth parameters: body length, head circumference, chest circumference, and arm circumference.
- ¹⁰ Neurological examinations include assessment of mental status, level of consciousness, sensory function, motor function, cranial nerve function, and reflexes.
- ¹¹ Neurological examinations will occur between 4 to 6 hours after the injection of study treatment or sham procedure.
- ¹² Blood chemistry, hematology, and urinalysis panels.
- ¹³ Samples for safety laboratory tests will be collected before the injection of study treatment or sham procedure on Days 64 and 183 only.
- ¹⁴ End of Part 1 safety laboratory tests may be performed locally in addition to centrally to accommodate the Part 2 Day 1 dosing.
- ¹⁵ Refer to [Table 5](#) for CSF PK sample schedule. The CSF samples will be analyzed for Nusinersen concentrations. The remaining CSF sample will be stored for optional future biomarker analyses.
- ¹⁶ Blood samples for PK assessment will be collected 4 hours (± 1 hour) after the injection of study treatment or sham procedure only on Day 1. Refer to [Table 5](#) for the plasma PK sample schedule.
- ¹⁷ Blood samples for PK assessment will be collected before the injection of study treatment or sham procedure on Days 64 and 183 only. Refer to [Table 5](#) for the plasma PK sample schedule.
- ¹⁸ Overnight stay (at least 24 hours) is required after the first injection of study treatment or sham procedure. Following all subsequent injections or sham procedures, a stay of at least 6 hours at the study site is required; overnight stays are optional on these days.
- ¹⁹ In addition to concomitant medications, ancillary procedures will be recorded.
- ²⁰ AEs and SAEs will be collected in the case report form from the time of signing of the informed consent form as described in [Section 15.3.1](#) and [Section 15.3.2](#).

CONFIDENTIAL

The information contained herein may not be used, disclosed, or published without the written consent of Biogen MA Inc.

4.2.2. Schedule of Events: Part 2

Table 3: Part 2 Schedule of Activities for Subjects Randomized to Receive Nusinersen in Part 1

Study Period	Part 2 Treatment/Follow-Up									
	Study Day	Day 1			Day 2 ¹	Days 120, 239, 358, 477, 596, 715 (± 7 days) ²			Days 121, 240, 359, 478, 597, 716 ¹	Part 2 Final Follow-Up (Day 835 [± 7 days]) ³ or Part 2 Early Termination ⁴

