Refer to **Error! Reference source not found.** for CSF PK sample schedule. The CSF samples will be analyzed for Nusinersen concentrations. The remaining CSF sample will be stored for optional future biomarker analyses.

Blood samples for PK assessment will be collected 4 hours ( $\pm 1$  hour) after the injection of study treatment or sham procedure only on Day 1. Refer to **Error! Reference source not found.** for the plasma PK sample schedule.

Blood samples for PK assessment will be collected before the injection of study treatment or sham procedure on Days 64 and 183 only. Refer to **Error! Reference source not found.** for the plasma PK sample schedule.

Overnight stay (at least 24 hours) is required after the first injection of study treatment or sham procedure. Following all subsequent injections or sham procedures, a stay of at least 6 hours at the study site is required; overnight stays are optional on these days.

In addition to concomitant medications, ancillary procedures will be recorded.

AEs and SAEs will be collected in the case report form from the time of signing of the informed consent form as described in Section and Section 15.3.2 of the protocol.

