### **5 Safety Data**

Analyses of safety data will include adverse events (Section 5.1), laboratory data (Section 5.2), ECGs (Section 5.3), vital signs (Section 5.4), and neurological examinations (Section 5.5).

Analyses of safety data will be based on the Safety Set. Baseline is defined as the last non-missing results prior to the first dose of Nusinersen or sham procedure.

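### The pNf-H baseline rule admits a post-dose Day 1 value, which matters for plasma, and change is summarised by original-scale means

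*SAP*

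**What the plan says.** **Samples.** SAP 4.8: "CSF and plasma samples collected as outlined in the schedule of events will be tested for pNf-H concentration". It does not say whether the plasma comes from the PK or the immunogenicity draws.

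**Baseline for pNf-H.** SAP 4.8 gives a first choice: "If any pNf-H measurement is non-missing prior to the first dose, the value closest to and prior to the first dose is used". It then gives the fallback: "If no pNf-H measurement is available prior to the first dose but any non-missing pNf-H measurement on Day 1 is collected, the value closest" in time becomes the baseline.

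**Baseline elsewhere.** Protocol Section 16 takes the last available value before the first dose of each part. SAP 3.2 says baseline is generally pre-dose. SAP 5, for safety data, says: "Baseline is defined as the last non-missing results prior to the first dose of Nusinersen or sham procedure".

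**Day 1 sampling in Part 1.** In Protocol Table 5 and SAP Table 3, pre-dose blood on Day 1 is marked not applicable, and the only Day 1 blood draw is at 4 hours. The footnotes agree: "Blood samples for PK assessment will be collected 4 hours" (SAP) and "after the injection of study treatment or sham procedure only on Day 1" (Protocol). CSF is pre-dose on every dosing day. The Part 1 activity tables also place an immunogenicity sample before dosing on Day 1, and SAP 7 shows that these samples are plasma.

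**Procedures by arm.** Of the sham procedure, Protocol 11.1.2 says: "The needle will break the skin, but no LP injection or needle insertion will occur". It adds that artificial CSF stands in for the sham child's CSF samples.

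**Summaries.** SAP 4.8.1 plots mean concentration on a semi-logarithmic scale, then says: "The mean change from baseline and percentage change from baseline, respectively will be presented on the original scale". SAP 2 provides medians, minima and maxima in general, and 95% confidence intervals for mean changes.

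**The concern.** A baseline measured after the intervention can already contain part of its effect. Here the Day 1 procedure differs by arm: an intrathecal injection with nusinersen, a skin prick with sham. If pNf-H moves at all within 4 hours of either, the baselines stop being comparable between arms, and each change value built on such a baseline carries the shift. The same baselines enter the Spearman correlations and p-values in SAP 4.8.1.

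Plasma is also the matrix that matters for comparison with sham. Sham CSF in Part 1 is artificial, so it can supply neither a pNf-H baseline nor a comparator, and the SAP does not exclude it.

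The second issue is the scale. Percentage change cannot go below -100% but has no upper limit. One child whose value doubles (+100%) and one whose value halves (-50%) average +25%, although the geometric change is zero. SAP 6.1 and 6.2 already include geometric means for drug concentrations.

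**Working it through.** The documents give no pNf-H variability, no effect of dosing or puncture on pNf-H, and no power figure, so there is nothing of the plan's own to reproduce. The first two steps compare the texts. The last two use assumed values, marked as such.

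**1. When the fallback applies.** It operates only if no pre-dose value exists, so the Day 1 value it selects must be post-dose.
- *CSF:* pre-dose at every dosing visit and never scheduled post-dose. The fallback should not arise for samples taken on schedule.
- *Plasma, PK draws assayed:* no pre-dose Day 1 sample exists in Part 1, so the 4-hour draw becomes baseline for everyone, up to 14 + 7 = 21 children.
- *Plasma, immunogenicity draws assayed:* a pre-dose Day 1 sample is scheduled, so the fallback is occasional.
- *Previous control, Part 2:* plasma from Days 64 and 183 (if reached) and End of Part 1 precedes the first nusinersen dose. The fallback is rarely needed if first dose means first nusinersen dose, but SAP 4.8 does not say so.

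**2. Windowing does not remove the problem.** SAP 4.1 labels study days up to and including Day 1 as Baseline for integrated CSF and plasma concentrations. A 4-hour Day 1 sample falls in that window.

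**3. Size of a baseline shift (assumed values).** Let *k* be the post-dose value divided by the pre-dose value on Day 1, and *g* the true geometric ratio to the pre-dose baseline. Observed change = 100 × (*g*/*k* − 1).

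| *k* | *g* = 1.0 | *g* = 0.5 |
|---|---|---|
| 0.8 | +25.0% | −37.5% |
| 1.0 | 0% | −50.0% |
| 1.25 | −20.0% | −60.0% |
| 1.5 | −33.3% | −66.7% |

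The error has no fixed sign. If *k* were 1.25 with nusinersen and 1.0 with sham, and nothing truly changed, the arms would differ by 20 percentage points from the baseline alone. If only 1 of 14 children used the fallback with *g* = 0.5, the mean would be 100 × [(13 × 0.5 + 0.5/*k*)/14 − 1]. That is −49.1% at *k* = 0.8 and −51.2% at *k* = 1.5, against −50%.

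**4. Mean percentage change (assumed lognormal ratio to baseline, log-SD *s*).** Expected mean = 100 × (*g* × exp(*s*²/2) − 1).

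| *s* | exp(*s*²/2) | *g* = 1.0 | *g* = 0.5 |
|---|---|---|---|
| 0.5 | 1.133 | +13.3% | −43.3% |
| 0.75 | 1.325 | +32.5% | −33.8% |
| 1.0 | 1.649 | +64.9% | −17.6% |

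In 100,000 simulated samples with *g* = 0.5, *s* = 0.8 and n = 14, the mean percentage change averaged −31.1%, the median −48.1% and the geometric estimate −48.9%. With n = 7 they averaged −31.1%, −46.6% and −47.6%.

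**The case against.** The other side has a good deal to say.

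- *The fallback is a last resort.* SAP 4.8 looks for a pre-dose value first, and its reference to the schedule of events can be read to include the pre-dose immunogenicity plasma. On that reading the fallback is rare and its effect small. This is a fair reading, but the SAP does not commit to it, and a rule that should rarely be needed can be removed at little cost.
- *The other baseline rules do not strictly govern pNf-H.* SAP 3.2 says generally, SAP 5 covers safety data, and the protocol lists no pNf-H endpoint. This stands: it is a departure from the plan's usual practice, given without a reason, rather than a direct contradiction.
- *No acute effect is documented.* The documents do not say that a puncture or the drug moves pNf-H within 4 hours. This stands too, so bias is possible but not shown.
- *The arithmetic mean percentage change is a legitimate quantity.* It answers a different question from the geometric ratio, and the planned medians would expose skew. This largely stands. What remains is that the presentation SAP 4.8.1 singles out is the mean, which is the summary most sensitive to a few large ratios in groups of 14 and 7.
- *A geometric ratio also fails at zero.* Correct. SAP 6.1 and 6.2 set drug concentrations below quantification to zero, and no rule is stated for pNf-H. The fix therefore needs one.

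**Conclusion.** The point holds in a limited form. The pNf-H rule permits a post-dose baseline. The exposure is in plasma and runs from rare to all Part 1 children, depending on an assay choice that the SAP leaves open. The size and sign of any resulting error cannot be derived from the documents; the *k* values above are illustrations. The upward pull of the mean percentage change is certain in direction if ratios to baseline are lognormal. Its size, +13% to +65% at no geometric change, rests wholly on the assumed log-SDs of 0.5 to 1.0.

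A reader might infer more, and the documents do not support it:

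- *That the pNf-H results are biased.* Neither the 4-hour effect nor the variability is given.
- *That every baseline follows a lumbar puncture.* Sham children in Part 1 have none, and scheduled CSF is drawn before dosing.
- *That the trial's only pharmacodynamic readout is compromised.* SAP 4.8.2 also foresees CSF SMN protein once an assay exists. pNf-H is the only biomarker with a specified analysis.

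pNf-H appears in neither document's list of endpoints, and no between-group test of it is planned. The priority is modest.

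**What to change.** **Baseline (SAP 4.8).**
- Delete the post-dose fallback.
- Define baseline separately for CSF and plasma as the last value before the first dose or sham procedure. For the Previous control, Part 2 group, use the last value before the first nusinersen dose.
- Name the pre-dose Day 1 immunogenicity plasma as the source of the Part 1 plasma baseline where volume and consent allow. Otherwise set the baseline to missing.
- Exclude artificial sham-arm CSF of Part 1 from all pNf-H summaries. The CSF baseline for these children is then their first real CSF, taken before dosing on Part 2 Day 1.

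**Summaries (SAP 4.8.1).** Report the geometric mean ratio to baseline with a 95% CI, computed on the log scale and back-transformed, in place of or beside the original-scale mean percentage change. State how values below quantification are handled.

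**Cost.** Mostly SAP wording and programming. The real downside is lost plasma baselines. No document gives the immunogenicity sample volume or what remains of it, and Protocol 11.1.1 allows storage of extra blood only with consent. If that plasma is unavailable, many children rather than a few could lack a plasma baseline. Plasma pNf-H should then be shown for them as concentrations over time, without change from baseline.
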